1.3. Statistical Hypotheses for Trial Objectives

The time to resolution of the 7 primary influenza-related symptoms, as assessed by a PRO measure (Flu-iiQ™), with pimodivir in combination with SOC treatment is statistically superior to treatment with placebo in combination with SOC treatment in subjects with influenza A infection who are at risk of developing complications.

1.4. Sample Size Justification

The study will aim to enroll 720 subjects, with 360 subjects per treatment arm.

The sample size is based on the primary endpoint of time to resolution of influenza-related symptoms. Time to resolution of influenza-related symptoms, ie, the proposed primary endpoint, will be based on the subjects' ratings on 7 items from the symptoms domain of the Flu-iiQ™ (cough, sore throat, headache, nasal congestion, feeling feverish, body aches and pains, and fatigue).

For the sample size, it is assumed that the recovery time is distributed similar to the time of symptom recovery in uncomplicated influenza, albeit with a somewhat longer average time to recovery due to the increased risk for complications and the increased time to recover for this population.

An underlying log-logistic distribution of the recovery time is assumed with a scale parameter of 0.55 and an intercept of 5.0 (in hours). Using the Gehan-Wilcoxon test to analyze the data and based on the assumption that the time to recovery is improved with 25%, a sample size of 600 subjects (randomized 1:1) will have an estimated power of 90% as based on 10,000 simulations. It is expected that approximately 15% of the total enrolled subjects may not be centrally-confirmed influenza A positive, resulting in a total of 720 subjects to be enrolled.

The effect of different distributional assumptions has been assessed, using estimates of the intercept and scale parameter from the accelerated failure time (AFT) model of time to resolution of influenza symptoms for both the log-logistic and log-normal distributions, based on data from the pimodivir Phase 2 Study 63623872FLZ2001. These estimates are provided in [Table 1](#). The scale parameter is a measure for variability of the recovery times. The intercept is a constant that cancels out in effect size estimation/simulations.

Table 1: Estimates of Intercept and Scale Parameter From Study 63623872FLZ2001

Model	Parameter	Estimate	95% CI
Log-logistic	Intercept	3.8546	(3.2000, 4.5092)
	Scale	0.5213	(0.4633, 0.5867)
Log-normal	Intercept	3.6277	(2.8897, 4.3656)
	Scale	0.9880	(0.8919, 1.0945)

For a trial with a sample size of 600 patients, recovery times were simulated based on the log-logistic model and separately also based on the log-normal distribution, assuming that the time to recovery is reduced by 25% in the pimodivir with SOC treatment arm compared to the placebo with SOC treatment arm, and that the subjects are randomized in a 1:1 ratio between the 2 treatment groups. To consider the variability in the intercept and scale parameters, the simulated recovery times were derived using the estimate of each parameter and using the upper limit of the 95% confidence interval (CI) for each parameter. A trial was simulated 10,000 times.

The Gehan-Wilcoxon test, log-logistic AFT model, and log-normal AFT model were used to analyze each of the 10,000 simulated datasets, for each recovery time distribution (log-logistic, log-normal) and for each parameter estimate (estimate, upper limit of the 95% CI). The power, for each statistical test, was estimated as the number of datasets where the 1-sided p-value from the test was <0.025 out of the 10,000 simulated datasets.

Table 2 provides the estimates of power for each statistical test and simulated time to resolution of influenza symptoms distributions.

Table 2: Estimated Power From 3 Statistical Tests

Simulated Distribution of Recovery Time	Estimated Power (%)		
	Gehan-Wilcoxon	AFT Log-logistic Model	AFT Log-normal Model
Log-logistic (estimate)	97.3	97.3	96.2
Log-logistic (upper CL)	93.3	93.4	91.3
Log-normal (estimate)	93.7	94.2	94.8
Log-normal (upper CL)	88.3	89.1	89.6

For the simulated recovery times based on the log-logistic model, the estimated power was greater than 90% when using both the estimate and the upper limit of the 95% CI for the intercept and scale parameter from the Phase 2 study.

For the simulated recovery times based on the log-normal model, the estimated power was greater than 90% and greater than 85% when using the estimate and the upper limit of the 95% CI, respectively, for the intercept and scale parameters from the Phase 2 study.

The sample size considerations are not based on accrual time and estimates of median survival times because all patients will have the same follow-up time by study design (28 days) and censoring is independent from time point of enrollment in the study, making accrual time not a concern. Also, the treatment effect is expressed as a 25% improvement (reduction) in time to resolution of influenza symptoms, and therefore does not require median times for sample size and power calculations.

1.5. Randomization and Blinding

Treatment Allocation: Procedures for Randomization

Central randomization will be implemented in this study. Subjects will be randomly assigned to 1 of 2 treatment arms in a 1:1 ratio based on a computer-generated randomization schedule prepared before the study by or under the supervision of the sponsor. The randomization will be balanced by using randomly permuted blocks and will be stratified by type of baseline SOC (including or not including influenza antiviral treatment) and time since onset of symptoms (first administration of study drug ≤ 48 hours or >48 hours since onset of influenza symptoms). The interactive web response system (IWRS) will assign a unique treatment code, which will dictate the treatment assignment and matching study drug kit for the subject. The requestor must use his or her own user identification and personal identification number when contacting the IWRS, and will then give the relevant subject details to uniquely identify the subject.

Blinding

The investigator will not be provided with randomization codes. The codes will be maintained within the IWRS, which has the functionality to allow the investigator to break the blind for an individual subject.

Data that may potentially unblind the treatment assignment (ie, study drug plasma concentrations) will be handled with special care to ensure that the integrity of the blind is maintained and the potential for bias is minimized. This can include making special provisions, such as segregating the data in question from view by the investigators, clinical team, or others as appropriate until the time of database lock and unblinding.

Under normal circumstances, the blind should not be broken until all subjects have completed the study and the database is finalized. Otherwise, the blind should be broken only if specific emergency treatment/course of action would be dictated by knowing the treatment status of the subject. In such cases, the investigator may in an emergency determine the identity of the treatment by contacting the IWRS. It is recommended that the investigator contact the sponsor or its designee if possible to discuss the particular situation, before breaking the blind. Telephone contact with the sponsor or its designee will be available 24 hours per day, 7 days per week. In the event the blind is broken, the sponsor must be informed as soon as possible. The date, time, and reason for the unblinding must be documented in the IWRS, in the appropriate section of the electronic case report form (eCRF) and in the source documents. The documentation received from the IWRS indicating the code break must be retained with the subject's source documents in a secure manner.

2. GENERAL ANALYSIS DEFINITIONS

All analysis dataset preparations and statistical analyses will be performed using SAS® version 9.2 or higher.

2.1. Visit Windows, Phase Definitions and Baseline

The study is set up as shown in [Figure 1](#). The phases will be constructed as shown in [Table 3](#).

Figure 1: Study time line.

Day	0	1	2	3	4	5	6	7	8	9	10	14	28
Arm 1	Scr.		Pimodivir 600 mg bid + SOC treatment				Follow-up						
Arm 2	Scr.		Placebo bid + SOC treatment				Follow-up						

Note: Depending on the time of screening/enrollment, subjects will receive 1 dose (evening) or 2 doses (morning and evening) of study drug on Day 1. For subjects who receive only 1 dose of pimodivir or placebo on Day 1 (evening), dosing should continue until the morning of Day 6 so that all subjects receive 10 doses in total.

2.1.1. Phase Definitions

Table 3: Construction of phases

Trial phase	Start date	End date
Screening (phase 1)	The date of signing the informed consent with 00:00 as a time part	1 minute before the first study drug intake
Treatment (phase 2) * ¹	Datetime of first study drug intake* ²	Datetime of last investigational medication intake* ² + 24 hours
Follow-up (phase 3)	End of the treatment phase +1 minute	Trial termination date (or date of last contact if later)

*¹: A treatment period will be constructed in the derived datasets with the same start and end date as the treatment phase.

*²: In case the time part of the medication intake is missing the imputed time part will be used as described below.

Additionally the treatment phase and follow-up phase will be combined in the analysis.

In case the time part of first medication intake is missing the randomization time will be used, if available. If the randomization time is also missing then the time part of first medication intake will be imputed with 8:00 if the first medication was taken in the morning or with 20:00 if the first medication was taken in the evening. In case the time of the last medication intake is missing, the time part will be imputed with 8:00 if the last medication was taken in the morning or with 20:00 if the last medication was taken in the evening.

The last phase, whichever it is for a subject, always ends on 23:59 of the day of trial termination (or date of last contact if later).

Assessments will be assigned to phases based on their start datetime, but seconds will not be taken into account. If only one assessment is expected per day and the day part of the start date of the assessment is present but the time part is missing, the assessment will be treated as if it happened

at 00:00 of the day of the assessment (except for Adverse Events see details in Section 7.1). No imputations on missing times/time parts will be made in the analysis datasets.

In case more than one assessment per day is expected and the time part is missing:

1. Allocate according to the timepoint: Morning=00:00, Evening=20:00
2. If 1 timepoint is missing on day x: Check the non-missing timepoint of the other record on this day x. Allocate this record to the timepoint of day x that is not already covered. Then apply 1.
3. If both timepoints are missing on day x: Allocate using the values of XXSPID, ie, lowest number is morning, highest number is evening. Then apply 1.

2.1.2. Analysis visits

In general, AVISIT will be derived as the day of a scheduled visit, assessment or self-assessment as recorded in the respective SDTM, including the safety follow-up visit and the Day 28 final study visit (eg, 'Day 4'). AVISITN will be the numeric counterpart (eg, for 'Day 4' AVISITN will be 4). The AVISIT for scheduled measurements before first intake will be set to 'Screening' with AVISITN = -1. For specifications on the baseline record and endpoint record see Section 2.5.

For post-baseline assessments of the FLU-iiQ™, Temperature (as recorded by the subject on the ePRO device), Daily Activities Resumption (Return to daily activity), Patient Global Impression of Severity (PGIS), Patient Global Impression of Change (PGIC) and the European Quality of Life 5 Dimensions (EQ-5D) questionnaires, AVISIT and AVISITN will be derived from the number of days in the study relative to the start of study treatment (reldy, see Section 2.4). Post-baseline assessments taken from 00:00 until 02:00 will be assigned to the day before (eg, a recording on Day 4 at 01:00 will be assigned AVISIT= Day 3).

2.1.3. Analysis timepoints

In general, for parameters that were assessed more than once daily, the analysis time point (ATPT) will be the time point as reported in the database.

For the PRO assessments of the FLU-iiQ™ and temperature all post-baseline records from day 1, 02:01 onwards will be assigned to an analysis time point (ATPT) using the following windows: morning = from 02:01 until 14:00 and evening = from 14:01 until 02:00. The measurements taken from 00:00 until 02:00 will be assigned to the evening of the day before (eg, a recording on Day 4 at 01:00 will be assigned AVISIT= Day 3, ATPT=Evening).

2.1.4. Use of records per analysis visit and timepoint

To ensure only one record is used per analysis visit and timepoint for the PRO assessments of the FLU-iiQ™ only one questionnaire (collection of questions answered on the same datetime) per analysis visit and timepoint should be selected for analysis. The selected questionnaire will be used for all analyses of all modules of the FLU-iiQ™ questionnaire. The following rules should be followed to select the questionnaire. Only questionnaires for which 50% of the items are available to construct a Composite symptom score are considered.

1. Determine the maximum score of the individual 7 primary influenza-related symptoms per questionnaire and select the questionnaire with the highest maximum score on an individual question.

2. If more than one questionnaire is still selected, the questionnaire which yields the highest composite symptom score based on 7 primary influenza-related symptoms within an analysis visit and timepoint is used.
3. If more than one questionnaire is still selected, the questionnaire latest in time is used.
4. If more than one questionnaire is still selected, the questionnaire with the highest sequence number is used.

To ensure only one record is used per analysis visit for the Return to daily activity and PGIS questionnaires only one questionnaire should be selected for analysis. Following rules should be followed to select the questionnaire.

1. The questionnaire latest in time is used.
2. If more than one questionnaire is still selected, the questionnaire with the highest sequence number is used.

To ensure only one record is used per analysis visit for the PGIC and EQ-5D questionnaires the following rules should be followed to select the questionnaire.

Listed below (Table 4) are the visit windows and the target days for each visit where PGIC and EQ-5D are recorded. The reference day is Study Day 1, the date of first intake of study drug.

1. If a subject has 2 or more actual visits in one visit window, the visit closest to the target day will be used as the protocol visit for that visit window.
2. If 2 actual visits are equidistant from the target day within a visit window, the later visit is used.

Table 4: Visit Windows for PGIC and EQ-5D

Scheduled Visit Number	Time Interval (label on output)	Time Interval (Day)*	Target Time Point (Day)
6	Day 6	[2 to 10]	6
14	Day 14	[11 to 20]	14
28	Day 28	[21 to 38]	28

*Relative to Study Day 1

To ensure only one record is used per analysis visit and analysis timepoint for the temperature, the following rules should be followed to select the temperature measurement.

1. The measurement with the highest temperature is used.
2. If more than one measurement is still selected, the measurement latest in time is used.
3. If more than one measurement is still selected, the measurement with the highest sequence number is used.

2.1.5. Unscheduled Assessments

In general, all scheduled assessments after first administration of study drug will be used. Unscheduled assessments will not be used in descriptive statistics or any per-time point analysis, but will be shown in listings as applicable. Pre-dose unscheduled assessments will be taken into

account for baseline determination and post first dose unscheduled assessments will be taken into account for worst-case determination.

For PRO assessments, both scheduled and unscheduled assessments will be taken into account to determine which assessment will be used per analysis visit/timepoint as described in Section 2.1.4.

For the time to response endpoints, recordings taken at unscheduled visits will be taken into account.

2.2. Analysis Sets

2.2.1. All Randomized Analysis Sets

2.2.1.1. All Randomized Analysis Set (RAND)

All randomized subjects with a randomization date time at or before the date time of first intake of study drug, or with a randomization date time and no study drug intake.

2.2.1.2. Randomized and/or Treated Analysis Set (RT)

All randomized subjects and/or all subjects who received at least 1 dose of study drug. The Randomized and/or Treated Analysis Set (RT) will be used in all listings unless specified otherwise for a specific display.

2.2.2. Efficacy Analysis Sets

Efficacy will be analyzed on the intent-to-treat infected (ITT-i) set and by randomized treatment. The primary efficacy endpoint will also be analyzed on the Per Protocol set. The primary efficacy endpoint and the two most important secondary endpoints (ie, 'Incidence of treatment-emergent adjudicated influenza complications' and 'Incidence of hospital admission 28 days after treatment initiation') will also be analyzed on the intent-to-treat non-infected (ITT-ni) set and by randomized treatment.

2.2.2.1. Intent-To-Treat infected (ITT-i) set

All subjects from the RAND analysis set who receive at least 1 dose of study drug and who have a confirmed infection with influenza A. Confirmation of influenza A infection will be obtained from virology data. If there are no virology data available at final analysis, then a subject will be excluded from the ITT-i set.

A subject is considered to have a confirmed infection with influenza A if he/she has:

- at least one positive PCR result from central lab testing at baseline or pre-baseline;

else

- at least two positive PCR results from central lab testing post-baseline.

Note: viral load (PCR) results from central lab testing recorded as 'TARGET NOT DETECTED' will be considered as negative, all other non-missing results as positive.

Note: if no viral load measurement is available prior to first dose of study drug, then the first result from the central lab testing obtained up to and including 30 minutes after first dose of study drug will be considered as the baseline assessment.

Note: viral load results from central lab testing obtained from leftover samples from the local virology test will be considered in determining confirmed infection with influenza A.

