  - n. The results of an earlier sample collected and tested positive for influenza A infection after the onset of symptoms, using a RIDT or, if available, a PCR-based or other rapid molecular diagnostic assay, can be used in lieu of the local virology testing at screening. This sample is used to determine eligibility.
  - o. Central virology testing: Nasal MT swabs should be obtained from the left and the right nostrils and pooled into the same collection tube. The samples will be collected at screening/baseline and on Days 3, 6, 10, and 14. The screening/baseline sample needs to be collected predose, as close as possible, to the first dose. Sampling should be done at approximately the same time ( $\pm 4$  hours) on each sampling day. Leftovers from nasal MT swabs collected for virology testing may be used for protein biomarker analysis.
  - p. At the time points where both nasal MT swabs and pharmacokinetic (PK) samples are obtained, these samples should be obtained as close together in time as possible.
  - q. Vital signs include body temperature, pulse rate, respiratory rate, and blood pressure.
  - r. The Flu-iiQTM questionnaire will be completed twice daily throughout the study; it will be programmed onto the electronic PRO (ePRO) device.
  - s. Questionnaire (Return to daily activities) to be completed at screening/baseline (as close as possible to first study drug intake) and then once daily onto the ePRO device.
  - t. Questionnaire PGIS to be completed from screening/baseline (as close as possible to the first study drug intake) and then once daily throughout Final Study Visit/Safety Follow-up Visit.
  - u. Questionnaire EQ-5D to be completed at screening/baseline (as close as possible to the first study drug intake); Questionnaires EQ-5D and PGIC to be completed on Day 6, 14, and 28 onto the ePRO device.
  - v. Follicle-stimulating hormone (FSH) will be tested at screening for female subjects who are amenorrheic for 12 months or less.
  - w. If feasible, safety blood samples will be collected after fasting for at least 10 hours.
  - x. The pharmacogenomic sample should preferably be collected at the specified time point, however if necessary it may be collected at a later time point without constituting a protocol deviation.
  - y. Sparse PK sampling will be performed as follows (if practically feasible):
    - On Day 3: at any time during the visit (date and time of last drug intake before PK sampling will be recorded).

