## ***Clinical Efficacy***

Refer to the IB for detailed info on the Phase 2a challenge study (Study VX11-787-101).

In Study 63623872FLZ2001 (community study), subjects received one of the 4 treatments for a total of 5 days: (1) pimodivir placebo bid + OST placebo bid, (2) pimodivir 300 mg bid + OST placebo bid, (3) pimodivir 600 mg bid + OST placebo bid, or (4) pimodivir 600 mg bid + OST 75 mg bid. Results from Study 63623872FLZ2001 showed that pimodivir was effective in decreasing viral loads (by quantitative real time polymerase chain reaction [qRT-PCR]) in subjects with a confirmed influenza A infection.

- The results showed an average change of AUC viral load (95% CI) (by qRT-PCR) vs placebo treatment of -3.6 (-7.1; -0.1), -4.5 (-8.0; -1.0), and -8.6 (-12; -5.1) day\*log10 copies/mL for the pimodivir 300 mg bid, pimodivir 600 mg bid, and pimodivir 600 mg bid + OST 75 mg bid treatment groups, respectively. The average change in AUC viral load of pimodivir 600 mg bid + OST 75 mg bid vs pimodivir 600 mg bid treatment was -4.1 (-7.4; -0.7) day\*log10 copies/mL. The primary analysis showed a statistically significant dose-response relationship of reduction in AUC viral load vs pimodivir dose.
- The results showed an average change on the AUC of viral load (95% CI) (by viral culture) vs placebo treatment of -2.1 (-2.9; -1.3), -2.1 (-2.8; -1.3), and -2.0 (-2.8; -1.2) log10 50% tissue culture infective dose (TCID50)/mL for the pimodivir 300 mg bid, pimodivir 600 mg bid, and pimodivir 600 mg bid + OST 75 mg bid treatment groups, respectively. The AUC viral load of pimodivir 600 mg bid + OST 75 mg bid and pimodivir 600 mg bid treatment was similar (0.1 [-0.7; 0.8]).
- There was a reduction of time to viral negativity vs placebo treatment of 13%, 18%, and 31% for the pimodivir 300 mg bid, pimodivir 600 mg bid, and pimodivir 600 mg bid + OST 75 mg bid treatment groups, respectively. The time to viral negativity was statistically significantly shorter for the pimodivir 600 mg bid and pimodivir 600 mg bid + OST 75 mg bid treatment groups compared to placebo treatment.

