- The difference (95% CI) in viral load (by qRT-PCR) AUC of pimodivir 600 mg bid + OST 75 mg bid treatment vs placebo bid + OST 75 mg bid treatment was  $0.7$  ( $-3.0, 4.3$ )  $\log_{10}$  viral particles (vp)/mL\*day. For subjects that were treated within 72 hours from onset of symptoms, the difference (95% CI) in AUC was  $-2.2$  ( $-8.0, 3.7$ )  $\log_{10}$  vp/mL\*day. For subjects that were treated within 96 hours from onset of symptoms, the difference (95% CI) in AUC was  $-0.9$  ( $-5.4, 3.6$ )  $\log_{10}$  vp/mL\*day.

- Ordinal Scale at Day 8

Overall, treatment with either placebo bid + OST 75 mg bid or pimodivir 600 mg bid + OST 75 mg bid resulted in a similar improvement in clinical status at Day 8, as expressed by a common odds ratio (95% CI) of 1.03 (0.43; 2.47). For subjects treated within 72 hours from onset of influenza symptoms, the estimated reduction of 0.60 in the odds, as expressed by a common odds ratio (95% CI) of 0.40 (0.09; 1.71), reflects an improvement in clinical outcome of 60%, with pimodivir 600 mg bid + OST 75 mg bid treatment compared to placebo bid + OST 75 mg bid treatment at Day 8. For subjects treated within 96 hours from onset of influenza symptoms, the estimated reduction of 0.50 in the odds, as expressed by a common odds ratio (95% CI) of 0.50 (0.16; 1.56), reflects an improvement in clinical outcome of 50%, with pimodivir 600 mg bid + OST 75 mg bid treatment compared to placebo bid + OST 75 mg bid treatment at Day 8.

- Influenza-related Complications

Overall, the incidence of influenza-related complications was 7.9% (5/63) and 15.6% (5/32) in the pimodivir 600 mg bid + OST 75 mg bid and placebo bid + OST 75 mg bid treatment groups, respectively. For subjects treated within 72 hours from onset of influenza symptoms, the incidence of influenza-related complications was 4.8% (1/21) and 26.7% (4/15) in the pimodivir 600 mg bid + OST 75 mg bid and placebo bid + OST 75 mg bid treatment groups, respectively. For subjects treated within 96 hours from onset of influenza symptoms, the incidence of influenza-related complications was 5.9% (2/34) and 23.8% (5/21) in the pimodivir 600 mg bid + OST 75 mg bid and placebo bid + OST 75 mg bid treatment groups, respectively.

- Time to Clinical Endpoints

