2.4. Study Day and Relative Day

Reference date refers to the start date of the first study drug administration. All efficacy and safety assessments at all visits will be assigned a day relative to this date.

The relative day (*reldy*) will be defined as:

$reldy = visit\ date - reference\ date + 1$ for visits on or after the reference date,

$reldy = visit\ date - reference\ date$ for visits before the reference date.

Consequently there is no 'day 0' defined.

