5.1. Analysis Specifications

5.1.1. Level of Significance

As a confirmatory strategy, to account for multiplicity in the statistical evaluation of the most important efficacy endpoints, hierarchical testing will be applied to control for overall Type I error. The following endpoints are included in the confirmatory strategy:

Primary Endpoint

- Time to resolution of the 7 primary influenza-related symptoms (cough, sore throat, headache, nasal congestion, feeling feverish, body aches and pains, fatigue)

Secondary Endpoints

- Incidence of complications associated with influenza after the start of study treatment
- Hospital admission rates 28 days after treatment initiation

First, the primary endpoint will be tested for superiority of pimodivir in combination with SOC over placebo in combination with SOC at the 2-sided 5% significance level. If superiority is shown on the primary endpoint, the first secondary endpoint in the sequence as indicated above will be tested for superiority at the same significance level. If superiority is shown for this secondary endpoint, the second (and last) secondary endpoint in sequence will be tested. In case superiority is not shown for an endpoint, no further endpoints in the sequence will be tested for superiority.

This testing procedure will be applied on the ITT-i set.

The final analysis on the ITT-i set (to support FDA marketing authorization approval) and the final analysis on the OST subset (to support marketing authorization approval in EMA) will be performed independently, using a 5% two-sided significance level for each.

Statistical Methodology for Evaluation at the Final Analysis

The p-values for the final analysis of the primary endpoint and the two most important secondary endpoints will be based on an inverse-normal combination test. For the primary endpoint, the p-values are obtained from the Gehan-Wilcoxon test. For incidence of complications associated with influenza after the start of study treatment and Hospital admission rates 28 days after treatment initiation the p-values will be obtained from a logistic regression model (see Sections 5.3.2 and 5.3.2.2).

All p-values below are one-sided p-values, to evaluate rejection of the null hypothesis that pimodivir is not better than placebo.

Let:

- p = p-value from the analysis of the ‘pre interim’ category of the ‘study period’ subgroup
- q = p-value from the analysis of the ‘post interim’ category of the ‘study period’ subgroup

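### Does admitting some subjects to ITT-i on PCR results obtained after dosing bias the primary analysis enough to need another analysis set?

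*SAP*

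**What the plan says.** SAP 2.2.2.1 (ITT-i set) has two routes to confirmed infection. The first is at least one positive central PCR at or before baseline. The second applies only when the first fails and asks for "at least two positive PCR results from central lab testing post-baseline". Two notes widen the first route. If no pre-dose sample exists, a result up to 30 minutes after the first dose counts as baseline. Also, "viral load results from central lab testing obtained from leftover samples from the local virology test will be considered" in establishing infection.

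On central swabs, footnote o of the Protocol Time and Events Schedule says: "The samples will be collected at screening/baseline and on Days 3, 6, 10, and 14". All scheduled post-baseline swabs therefore fall during or after treatment.

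ITT-i is the main efficacy set, and SAP 5.1.1 says of the hierarchy: "This testing procedure will be applied on the ITT-i set". On other sets, SAP 2.2.2 states: "The primary efficacy endpoint will also be analyzed on the Per Protocol set". The primary and two key secondary endpoints are also analysed on ITT-ni, which is the treated, randomised subjects without confirmation. The sensitivity analyses in SAP 5.2.3 concern missing questionnaires only.

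**The concern.** Membership of a primary analysis set should rest on information that treatment cannot alter. For subjects without a pre-dose positive it does not: they must still be shedding on at least two post-dose swabs. Protocol 1.1 (Clinical Efficacy) reports that time to viral negativity in the Phase 2b community study was 18% shorter on 600 mg than on placebo. A fast clearer on pimodivir could therefore miss ITT-i where the same person on placebo would have entered.

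The arms of ITT-i would then differ slightly by selection, in the set that carries the primary test and both hierarchical secondary tests. Per Protocol is a subset of ITT-i and ITT-ni is its complement, so neither shows the comparison without the fallback subjects. If the group were large and clearance tracked symptom recovery closely, the estimate could be distorted.

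**Working it through.** **The plan's own figure.** SAP 1.4 goes from 600 evaluable to 720 enrolled, allowing for 15% not centrally confirmed. 600/0.85 = 706, within 2% of 720; and 720 × 0.85 = 612, or 306 per arm.

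**Chance of entering by the fallback.** The documents give no shedding distribution, so this part is assumed: placebo median time to PCR negativity m = 7 days (range 6 to 8), log-logistic with scale 0.5, clearance without relapse, and an 18% shorter time on pimodivir. On day counting, SAP 2.4 says "Reference date refers to the start date of the first study drug administration" and numbers that date Day 1, so the Day 6 swab falls 5 days after the first dose. With clearance in one direction, two positives means still positive at Day 6:

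P = 1 / (1 + (5/m)²)

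- Placebo, m = 7: 1/(1 + 0.510) = 0.662
- Pimodivir, m = 7 × 0.82 = 5.74: 1/(1 + 0.759) = 0.569
- m = 6 and 4.92: 0.590 and 0.492
- m = 8 and 6.56: 0.719 and 0.633
- Visit moved to Day 7 (6 days after the first dose), m = 7 and 5.74: 0.58 and 0.48

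**Numbers entering** (306 × share × P) **and the effect on the primary result.** The simulation used 4,000 trials per setting. Symptom times were log-logistic (intercept 5.0, scale 0.55, as in SAP 1.4), capped at 27 days, with true ratio 0.75. Clearance and symptom times were linked by a Gaussian copula with correlation 0.3 or 0.6. The Wilcoxon test was unstratified.

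| Infected with no pre-dose positive (assumed) | Fallback entries, placebo / pimodivir | Median ratio, current rule (correlation 0.3; 0.6) | Power, current rule vs pre-dose only (0.3; 0.6) |
|---|---|---|---|
| 5% | 10 / 9 | 0.750; 0.750 | 95.5 vs 95.2; 95.9 vs 95.4 |
| 10% | 20 / 17 | 0.751; 0.752 | 95.3 vs 94.1; 95.3 vs 94.3 |
| 30% | 61 / 52 | 0.751; 0.757 | 93.9 vs 87.8; 92.5 vs 86.3 |

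The largest shift is 0.757/0.75 = 1.009, toward no effect. That is the expected direction, because the pimodivir subjects left out are the fast clearers, who also tend to recover sooner.

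**Type I error.** With a true ratio of 1.0, one-sided error was 2.2% to 3.1% under either rule, with no pattern (simulation SE 0.25 points). A separate null simulation used a log-normal model with median shedding of 5 days, shares of 5% and 15%, and shedding ratios of 0.82 and 0.69. It gave 2.3% to 2.8% for the current rule.

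**Cost of requiring pre-dose confirmation.** From the table, the power loss is 0.3 to 0.5 points at 5%, 1.0 to 1.2 at 10%, and 6.1 to 6.2 at 30%. An analytic check uses power = Φ(|ln 0.75| / (s√3) × √(N/4) − 1.96). It reproduces the log-logistic Gehan-Wilcoxon entries of SAP Table 2 (97.4% against 97.3%; 93.4% against 93.3%). At s = 0.55 and N = 600 it gives 95.9%, not the 90% stated in the text; that discrepancy does not bear on this point. If 10% of the 612 were fallback entrants and were dropped, N = 551 and power falls from 96.2% to 94.3%.

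**What the plan already shows.** Influenza A subtype comes from the baseline sample (Protocol 9.2.1.3) and is a subgroup for the primary and both key secondary endpoints (SAP 2.3). Baseline polymorphism and baseline resistance are subgroups for the primary endpoint. These partly select subjects with virus at baseline. SAP 4.1 tabulates baseline qRT-PCR negativity, and with the missing results this bounds the number of fallback entrants from above. SAP 4.2 gives set sizes by planned arm.

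**The case for a change.** The strongest case for a change is one of principle and price. Part of the primary set is chosen on a post-randomisation result. The baseline-virus subgroups are not a pre-dose-confirmed population, ITT-i and ITT-ni are never pooled, and the entry route is not counted. A sensitivity run in subjects confirmed at or before baseline, with a count by arm, would use existing data and leave the primary analysis alone. For time to viral negativity, which has a superiority objective, the fallback selects on the outcome itself.

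All of that is accurate. But viral negativity lies outside the hierarchy, and leaving out fast clearers on pimodivir works against the drug there too. For the confirmatory endpoints, the extra run would only display an effect already expected to be negligible.

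The numbers have weak points. The shedding median and scale are assumptions, and the model suits a missing baseline swab better than a falsely negative one. The 306 per arm is treated as infected before fallback failures are removed, although SAP 1.4 describes it as already confirmed. The simulated test is unstratified and single-stage, unlike the planned one. The Phase 2b bullet does not name its assay. In the hospital study, on top of oseltamivir, the PCR area-under-the-curve difference was 0.7 (95% CI −3.0 to 4.3), so the dependence on treatment may be weaker in subjects taking an antiviral. None of these gives reason to expect a large bias in pimodivir's favour.

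**Conclusion.** The reading of the text is right, but no change follows. The fallback is a fair trade-off: it keeps infected subjects whose pre-dose central result is missing or falsely negative, in line with the estimand's population of confirmed influenza A (SAP 5.2.2). The leftover-sample and 30-minute provisions limit how many subjects need it.

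Under the stated shedding assumptions, the primary estimate moves by about 1% at most even if 30% of infected subjects lacked a pre-dose positive. It moves by 0.3% or less (0.752/0.75) at 5% to 10%. The direction is against pimodivir and type I error is not inflated, so a false superiority claim is not the risk.

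Redefining ITT-i would exchange this for up to about 6 points of power. It would also change the set behind the pre-interim p-value in the combination test (SAP 5.1.1) after the interim cut of 28 February 2020 given in SAP 2.3. A count of fallback entries or an extra run would be harmless, but a sound conclusion does not depend on either. The judgement rests on the fallback share, which the documents do not give, being no larger than the range examined.
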